#### Serious Adverse Event Paper Reporting Process

In case of a serious adverse event (SAE) the investigator must report this immediately, and under no circumstances later than 24 hours following the knowledge of the SAE to:

E-mail: **CCI**

or

**CCI** Medical Affairs SAE Fax #: **CCI**

For fatal or life-threatening events, copies of hospital case reports, autopsy reports, and other documents are also to be submitted by e-mail or fax when requested and applicable. Transmission of such documents should occur without personal subject identification, maintaining the traceability of a document to the subject identifiers.

Additional information may be requested to ensure the timely completion of accurate safety reports.

Any medications necessary for treatment of the SAE must be recorded onto the concomitant medication section of the subject's CRF/eCRF and the event description section of the SAE form.

After the last Study Drug intake, and for all patients under Standard of Care, the investigator is highly encouraged to report any AE/SAE considered as related to the Standard of Care medication directly to the marketing authorization holder and/or its National Competent Authority.

In order to avoid duplication in the reporting of such events, the Sponsor will not report these events simultaneously.

#### **7.4. Sponsor Reporting Requirements**

Depending on relevant local legislation or regulations, including the applicable US FDA Code of Federal Regulations, the EU Clinical Trials Directive (2001/20/EC) and relevant updates, and other country-specific legislation or regulations, the sponsor may be required to expedite to worldwide regulatory agencies reports of SAEs, serious adverse drug reactions (SADRs), or SUSARs. In accordance with the EU Clinical Trials Directive (2001/20/EC), the sponsor or a specified designee will notify worldwide regulatory agencies and the relevant IEC in concerned Member States of applicable SUSARs as outlined in current regulations.

Assessment of expectedness for filgotinib SAEs will be determined by the Sponsor using reference safety information specified in the investigator's brochure. Methotrexate may be used as standard of care therapies in this study; consequently, any SAEs that are attributed to methotrexate or any other concomitant treatment will be forwarded by the investigator to its respective marketing authorization holder.

All investigators will receive a safety letter notifying them of relevant SUSAR reports associated with any study IMP. The investigator should notify the IRB or IEC of SUSAR reports as soon as is practical, where this is required by local regulatory agencies, and in accordance with the local institutional policy.

## **7.5. Clinical Laboratory Abnormalities and Other Abnormal Assessments**

Laboratory abnormalities are usually not recorded as AEs or SAEs. However, laboratory abnormalities (eg, clinical chemistry, hematology, and urinalysis) independent of the underlying medical condition that require medical or surgical intervention or lead to IMP interruption or discontinuation must be recorded as an AE, as well as an SAE, if applicable. In addition, laboratory or other abnormal assessments (eg, electrocardiogram, X-rays, vital signs) that are associated with signs and/or symptoms must be recorded as an AE or SAE if they meet the definition of an AE (or SAE) as described in Sections 7.1.1 and 7.1.2. If the laboratory abnormality is part of a syndrome, record the syndrome or diagnosis (ie, anemia) not the laboratory result (ie, decreased hemoglobin).

Severity should be recorded and graded according to the CTCAE.

For AEs associated with laboratory abnormalities, the event should be graded on the basis of the clinical severity in the context of the underlying conditions; this may or may not be in agreement with the grading of the laboratory abnormality.

## **7.6. Toxicity Management**

All clinical and clinically significant laboratory toxicities will be managed according to uniform guidelines detailed in [Appendix 14](#) and as outlined below.

Refer to Section 3.7, Criteria for Study Drug Interruption or Discontinuation, for additional specific discontinuation criteria. Specific toxicity discontinuation criteria in Section 3.7 supersede below general toxicity guidelines, and in general, where discrepancy is present, the more conservative criteria apply. The Sponsor Medical Leader or designee should be consulted prior to study drug discontinuation when medically feasible.

### **7.6.1. Grades 1 and 2 Laboratory Abnormality or Clinical Event**

Continue study drug at the discretion of the investigator.

- For study specific interruption and stopping criteria, please refer to Section 3.7 (Criteria for Interruption or Discontinuation of Study Treatment)
- For Grades 1 and 2 Laboratory Abnormality or Clinical Event not specified in Section 3.7, continue study drug at the discretion of the investigator.

### **7.6.2. Grades 3 Laboratory Abnormality or Clinical Event**

- For study specific interruption and stopping criteria, please refer to Section 3.7 (Criteria for Interruption or Discontinuation of Study Treatment)
- For Grades 3 Laboratory Abnormality or Clinical Event not specified in Section 3.7, the following toxicity management guidelines apply:

- For Grade 3 clinically significant laboratory abnormality or clinical event, IMP may be continued if the event is considered to be unrelated to IMP.
- For a Grade 3 clinical event, or clinically significant laboratory abnormality confirmed by repeat testing, that is considered to be related to IMP, IMP should be withheld until the toxicity returns to  $\leq$  Grade 2.

If a laboratory abnormality recurs to  $\geq$  Grade 3 following re-challenge with IMP and is considered related to IMP, then IMP should be permanently discontinued and the subject managed according to local clinical practice. Recurrence of laboratory abnormalities considered unrelated to IMP may not require permanent discontinuation.

### **7.6.3. Grades 4 Laboratory Abnormality or Clinical Event**

- For study specific interruption and stopping criteria, please refer to Section 3.7 (Criteria for Interruption or Discontinuation of Study Treatment).
- For Grade 4 Laboratory Abnormality or Clinical Events not specified in Section 3.7, the following toxicity management guidelines apply:
  - For a Grade 4 clinical event or clinically significant Grade 4 laboratory abnormality confirmed by repeat testing that is considered related to IMP, IMP should be permanently discontinued and the subject managed according to local clinical practice. The subject should be followed as clinically indicated until the laboratory abnormality returns to Baseline or is otherwise explained, whichever occurs first. A clinically significant Grade 4 laboratory abnormality that is not confirmed by repeat testing should be managed according to the algorithm for the new toxicity grade.

IMP may be continued without dose interruption for a clinically non-significant Grade 4 laboratory abnormality (eg, Grade 4 CK after strenuous exercise or triglyceride elevation that is nonfasting or that can be medically managed) or a clinical event considered unrelated to IMP.

Treatment-emergent toxicities will be noted by the investigator and brought to the attention of the Sponsor Medical Leader or designee, who will have a discussion with the investigator and decide the appropriate course of action. Whether or not considered treatment-related, all subjects experiencing AEs must be monitored periodically until symptoms subside, any abnormal laboratory values have resolved or returned to Baseline levels or they are considered irreversible, or until there is a satisfactory explanation for the changes observed.

Any questions regarding toxicity management should be directed to the Sponsor Medical Leader or designee.

## **7.7. Special Situations Reports**

### **7.7.1. Definitions of Special Situations**

Special situation reports include all reports of medication error, abuse, misuse, overdose, product complaints, occupational exposure, drug interactions, unexpected benefit, transmission of

infectious agents via the product, counterfeit or falsified medicine, exposure via breastfeeding, and partner pregnancy reports regardless of an associated AE.

Medication error is any unintentional error in the prescribing, dispensing, preparation for administration or administration of a medicinal product while the medication is in the control of the health care professional, patient, or consumer. Medication errors may be classified as a medication error without an AE, which includes situations of missed dose; medication error with an AE; intercepted medication error; or potential medication error.

Abuse is defined as persistent or sporadic intentional excessive use of a medicinal product by a subject.

Misuse is defined as any intentional and inappropriate use of a medicinal product that is not in accordance with the protocol instructions or the local prescribing information.

An overdose is defined as an accidental or intentional administration of a quantity of a medicinal product given per administration or cumulatively which is above the maximum recommended dose as per protocol or in the product labelling (as it applies to the daily dose of the subject in question). In cases of a discrepancy in drug accountability, overdose will be established only when it is clear that the subject has taken the excess dose(s). Overdose cannot be established when the subject cannot account for the discrepancy except in cases in which the investigator has reason to suspect that the subject has taken the additional dose(s).

Occupational exposure is defined as exposure to a medicinal product as a result of one's professional or non-professional occupation.

Drug interaction is defined as any drug/drug, drug/food, or drug/device interaction.

Unexpected benefit is defined as an unintended therapeutic effect where the results are judged to be desirable and beneficial.

Transmission of infectious agents is defined as any suspected transmission of an infected agent through an IMP.

Product complaint is defined as complaints arising from potential deviations in the manufacture, packaging, or distribution of the medicinal product.

Counterfeit or falsified medicine: Any investigational product with a false representation of: a) its identity, b) its source, or c) its history.

## **7.7.2. Instructions for Reporting Special Situations**

### **7.7.2.1. Instructions for Reporting Partner Pregnancies**

Pregnancies of female partners of male study subjects exposed to study drug must be reported until 90 days after the last study drug intake and relevant information should be submitted to the Sponsor using the pregnancy and pregnancy outcome forms within 24 hours. If the end of the pregnancy occurs after the study has been completed, the outcome should be reported directly to:

E-mail: **CCI** [REDACTED]

or

**CCI** Medical Affairs SAE Fax #: **CCI** [REDACTED]

After 90 days from the last Study Drug intake, and if the patient is under Standard of Care treatment, the investigator is highly encouraged to report any Pregnancy considered as related to this Standard of Care treatment directly to the marketing authorization holder and/or its National Competent Authority.

In order to avoid duplication in the reporting of such events, the sponsor will not report these Pregnancies simultaneously.

Refer to [Appendix 10](#) for Pregnancy Precautions, Definition of Females of Childbearing Potential and Contraceptive Requirements.

#### **7.7.2.2. Reporting Other Special Situations**

All other special situation reports must be reported on the special situations report form and forwarded to the Sponsor within 24 hours of the investigator becoming aware of the situation. These reports must consist of situations that involve study IMP.

Special situations involving concomitant medications does not need to be reported on the special situations report form; however, for special situations that result in AEs due to a concomitant medication, the AE should be reported on the AE form.

Any inappropriate use of concomitant medications prohibited by this protocol should not be reported as “misuse,” but may be more appropriately documented as a protocol deviation.

Refer to Section [7.3](#) and the CRF/eCRF completion guidelines for full instructions on the mechanism of special situations reporting.

All clinical sequelae in relation to these special situation reports will be reported as AEs or SAEs at the same time using the AE CRF/eCRF and/or the SAE report form. Details of the symptoms and signs, clinical management, and outcome will be reported, when available.

## **8. STATISTICAL CONSIDERATIONS**

### **8.1. Analysis Objectives and Endpoints**

#### **8.1.1. Analysis Objectives**

The primary objective of this study is:

- To evaluate the effect of filgotinib on testicular function as defined by the proportion of subjects with a  $\geq 50\%$  decrease from Baseline in sperm concentration at Week 13

The secondary objectives of this study include:

- To evaluate the effect of filgotinib on testicular function as defined by the proportion of subjects with a  $\geq 50\%$  decrease from Baseline in sperm concentration at Week 26
- To evaluate the effect of filgotinib on sperm total motility at Weeks 13 and 26
- To evaluate the effect of filgotinib on total sperm count at Weeks 13 and 26
- To evaluate the effect of filgotinib on the change from Baseline in sperm concentration at Weeks 13 and 26
- To evaluate the effect of filgotinib on ejaculate volume at Weeks 13 and 26
- To evaluate the effect of filgotinib on sperm morphology at Weeks 13 and 26

The exploratory objectives of this study include:

- To evaluate the reversibility of observed effects of filgotinib on testicular function in subjects who experience a  $\geq 50\%$  decrease in sperm concentration, and/or motility, and/or morphology
- To evaluate the effect of filgotinib on sex hormones, including LH, FSH, inhibin B, and total testosterone at Weeks 13 and 26
- To evaluate the safety and tolerability of filgotinib
- To characterize the plasma PK of filgotinib and its metabolite (GS-829845, formerly CCI [REDACTED])

### **8.1.2. Primary Endpoint**

The primary endpoint is the proportion of subjects with a  $\geq 50\%$  decrease from Baseline in sperm concentration at Week 13.

### **8.1.3. Secondary Endpoints**

The secondary endpoints are:

- The proportion of subjects with a  $\geq 50\%$  decrease from Baseline in sperm concentration at Week 26
- Change from Baseline in percent motile sperm at Weeks 13 and 26
- Change from Baseline in total sperm count at Weeks 13 and 26
- Change from Baseline in sperm concentration at Weeks 13 and 26

- Change from Baseline in ejaculate volume at Weeks 13 and 26
- Change from Baseline in percent normal sperm morphology at Weeks 13 and 26

#### **8.1.4. Exploratory Endpoints**

The exploratory endpoints are:

- Percent of subjects who achieve reversibility among subjects who experience a  $\geq 50\%$  decrease in sperm concentration, and/or motility, and/or morphology
- Change from Baseline in sex hormones, including LH, FSH, inhibin B, and total testosterone at Weeks 13 and 26
- PK characteristics for filgotinib and its metabolite GS-829845

### **8.2. Analysis Conventions**

#### **8.2.1. Analysis Sets**

##### **8.2.1.1. All Randomized Set**

The All Randomized Set includes all subjects who were randomized.

##### **8.2.1.2. Semen Analysis Set**

The Semen Analysis Set includes all randomized subjects who have Baseline and at least one post-Baseline semen sample. This is the primary analysis set for semen-related parameters.

##### **8.2.1.3. Safety Analysis Set**

The Safety Analysis Set includes all subjects who received at least one dose of study drug. This is the primary analysis set for safety endpoints.

##### **8.2.1.4. Pharmacokinetic Analysis Set**

The PK analysis set includes all subjects in the Safety Analysis Set who have at least 1 nonmissing postdose concentration value for filgotinib and/or its metabolite GS-829845. This is the primary analysis set for all PK analyses.

### **8.3. Data Handling Conventions**

PK concentration values and PK parameter values below the limit of quantitation (BLQ) will be presented as “BLQ” in the data listings. BLQ values that occur prior to the first dose will be treated as 0, BLQ values at all other time points will be treated as 1/2 of the lower limit of quantitation (LLOQ).

Laboratory data that are continuous in nature but are less than the LLOQ or above the upper limit of quantitation will be imputed to the value of the lower or upper limit minus or plus one

significant digit, respectively (eg, if the result of a continuous laboratory test is <20, a value of 19 will be assigned; if the result of a continuous laboratory test is <20.0, a value of 19.9 will be assigned).

In general, missing data will not be imputed unless methods for handling missing data are specified. To assess missing semen data patterns, missingness by treatment arm, randomization stratum and Baseline demographic characteristics will be summarized. Additional details on handling missing data and sensitivity analyses will be provided in the statistical analysis plan (SAP).

#### **8.4. Demographic Data and Baseline Characteristics**

Demographic and Baseline characteristics will be summarized by treatment group using standard descriptive statistics including sample size, mean, standard deviation (SD), median, Q1, Q3, minimum, and maximum for continuous variables and numbers and percentages for categorical variables.

Demographic data will include sex, race, ethnicity, and age.

Baseline characteristics may include sperm concentration, ejaculate volume, total sperm per ejaculate, and other variables of interest.

#### **8.5. Statistical Analysis**

##### **8.5.1. Primary Analysis**

The primary endpoint is the proportion of subjects with a  $\geq 50\%$  decrease from Baseline in sperm concentration at Week 13. A cumulative distribution plot for the percent change from Baseline in sperm concentration at Week 13 for each treatment group will be constructed. The x-axis will display percent changes from Baseline in sperm concentration ranging from 100% decrease (ie, -100 % or azoospermia) to the maximal observed increase. The y-axis will display the proportion of subjects who experienced a percentage change in sperm concentration equal to or less than the corresponding x-axis value at Week 13. This method is suggested in FDA's Guidance on Testicular toxicity (October 2018). The proportion of subjects experiencing at least a 50% decrease in sperm concentration from Baseline will be calculated for each treatment group. The difference between the filgotinib and placebo groups will be calculated together with the associated 95% confidence interval.

Subjects who have two samples available at Week 13, will be included in the primary analysis. Sensitivity analyses will be performed to evaluate the impact of different missing data patterns on the primary analysis. Details of the sensitivity analyses will be provided in the SAP.

##### **8.5.2. Secondary Analyses**

The secondary endpoints include the proportion of subjects with a  $\geq 50\%$  decrease from Baseline in sperm concentration at Week 26, changes from Baseline at Weeks 13 and 26 in sperm concentration, total sperm count, ejaculate volume, percent motile sperm, and percent normal sperm morphology.

The continuous endpoints will be summarized (n, mean, SD, median, Q1, Q3, minimum, and maximum) by treatment group at Weeks 13 and 26 along with corresponding change from Baseline and 95% CIs. All categorical endpoints will be summarized by the number and percentage of subjects who meet the endpoint definition.

An analysis of covariance (ANCOVA) model adjusting for Baseline value and stratification factors will be used to estimate treatment differences (95% CI) for the continuous endpoints. The categorical endpoint at Week 26 will be summarized descriptively.

#### **8.5.3. Exploratory Analyses**

The exploratory analyses of sex hormones will use the same analysis methods used as for the continuous secondary endpoints. For reversibility, the number and percentage and cumulative number and percentage of subjects who achieve reversibility will be displayed by sperm parameter and monitoring phase visit for those subjects with a  $\geq 50\%$  decrease in the sperm parameter(s) qualifying them for entry into the monitoring phase.

#### **8.5.4. Other Safety Analysis**

All other safety analyses will be performed using the Safety Analysis Set.

Safety will be evaluated by assessment of clinical laboratory tests, PEs, ECG and vital signs measurements at various time points during the study, and by the documentation of AEs.

All safety data collected on or after the first dose of study drug administration up to 30 days after the last dose of study drug, unless specified otherwise, will be summarized by treatment group according to the study drug received.

#### **8.5.5. Extent of Exposure**

A subject's extent of exposure to study drug will be generated from the study drug administration page of the eCRF. Exposure data will be summarized by treatment group.

Duration of exposure to study drug will be expressed as the number of weeks between the first and last dose of the study drug, inclusive, regardless of temporary interruptions in study drug administration and summarized by treatment group.

#### **8.5.6. Adverse Events**

Clinical and laboratory AEs will be coded using the Medical Dictionary for Regulatory Activities (MedDRA). System Organ Class, High-Level Group Term (HLGT), High-Level Term (HLT), PT, and Lower Level Term (LLT) will be attached to the clinical database.

TEAEs are:

- Any AEs with an onset date of on or after the study drug start date and no later than 30 days after permanent discontinuation of study drug or

- Any AEs leading to premature discontinuation of study drug.

Summaries (number and percentage of subjects) of TEAEs by system organ class and PT will be provided by treatment group. TEAEs will also be summarized by relationship to study drug and severity. In addition, TEAEs leading to premature discontinuation of study drug will be summarized and listed.

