Study Drug	Study drug is defined as blinded filgotinib or placebo during the Double-blind Treatment Phase and open-label filgotinib during the Extension Phase.
First unblinded interim analysis (IA1)	Unblinded Week 26 analysis to be performed after at least 200 evaluable subjects pooled across studies GS-US-418-4279 (GLPG0634-CL-228) and GLPG0634-CL-227 complete Week 13 and evaluable subjects from Study GLPG0634-CL-227 complete Week 26 or permanently discontinue from study drug. Referred to as 'Week 26 Analysis' in the SAP.
Second unblinded interim analysis (IA2)	Unblinded Week 26 analysis to be performed after all subjects reach Week 26 and all subjects with a $\geq 50\%$ decrease in sperm concentration, and/or motility, and/or morphology up to Week 26 enter the Monitoring Phase and either meet reversibility criteria or are followed off-treatment for 52 weeks, whichever occurs first. Referred to as 'Week 26 and Reversibility Analysis for Pre-specified Sperm Decreases Up to Week 26' in the SAP.

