### **7.2.1. Assessment of Causality for Study Drugs and Procedures**

The investigator or qualified subinvestigator is responsible for assessing the relationship to IMP therapy using clinical judgment and the following considerations:

**No:** Evidence exists that the adverse event has an etiology other than the study drug. For SAEs, an alternative causality must be provided (eg, pre-existing condition, underlying disease, intercurrent illness, or concomitant medication).

**Yes:** There is reasonable possibility that the event may have been caused by the IMP.

It should be emphasized that ineffective treatment should not be considered as causally related in the context of adverse event reporting.

The relationship to study procedures (eg, invasive procedures such as venipuncture or biopsy) should be assessed using the following considerations:

**No:** Evidence exists that the adverse event has an etiology other than the study procedure.

**Yes:** The adverse event occurred as a result of protocol procedures, (eg, venipuncture).

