8.1.3. Relationship of Adverse Events to Study Drug

Related AEs are those for which the investigator selected “Related” on the AE eCRF to the question of “Related to Study Treatment.” For the extension phase, AEs marked as “Related to SOC” will be considered as related for subjects who switch to SOC in the extension phase. Relatedness will always default to the investigator’s choice, not that of the medical monitor. Events for which the investigator did not record relationship to study drug will be considered related to study drug for summary purposes. However, by-subject data listings will show the relationship as missing.

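### In the extension-phase tables, treatment-related means study drug in the open-label filgotinib column but study drug or Standard of Care in the other two, so filgotinib-attributed events after the switch cannot be separated

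*Protocol*

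**What the plan says.** **Protocol.** Section 7.2.1 says the investigator "is responsible for assessing the relationship to IMP therapy using clinical judgment". It adds one other causality question, on study procedures, and none on SoC. The Definition of Terms fixes the object of the drug question: "Study drug is defined as blinded filgotinib or placebo during the Double-blind Treatment Phase and open-label filgotinib during the Extension Phase". Section 8.5.6 then plans the summary: "TEAEs will also be summarized by relationship to study drug and severity". The same section ends the treatment-emergent window 30 days after permanent discontinuation of study drug, apart from events that lead to discontinuation.

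**SAP.** Section 8.1.3 starts from the investigator's answer on relationship to study treatment and adds two rules:

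- Extension-phase AEs marked as related to SoC "will be considered as related for subjects who switch to SOC in the extension phase".
- "Events for which the investigator did not record relationship to study drug will be considered related to study drug for summary purposes". This rule is not limited to any phase or sequence.

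Section 3.2 sets three extension-phase safety columns: filgotinib to open-label filgotinib, filgotinib to SoC, and placebo to SoC. Section 8.1.6 reports treatment-related AEs (all, Grade 2 or higher, Grade 3 or higher) and treatment-related SAEs in those columns, without splitting them by what the event was attributed to. Section 6.7, which lists changes from the protocol, covers semen and hormone data only.

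**The concern.** A reader will compare the treatment-related row across the three columns, and the row does not have one meaning. Two things are at stake.

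First, men who leave filgotinib for SoC are the group in whom late events attributed to filgotinib would appear. Their column adds those events to events attributed to the new therapy.

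Second, the same drug reaction can be classified differently by column. Protocol 7.4 notes that "Methotrexate may be used as standard of care therapies in this study", while Protocol 5.3.1 lets methotrexate continue as background and Protocol 3.2 lets background treatment alongside open-label filgotinib be adjusted. An event blamed on methotrexate can count as related in a SoC column and not in the open-label filgotinib column. The SAP does not declare any of this as a departure from Protocol 8.5.6.

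**Working it through.** The plan states no figure on this point, so there is none to reproduce. The check sets the rules side by side and then gives an illustrative size.

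**1. What counts as related, by column (SAP 8.1.3 with 3.2)**

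| Investigator's answer | Filgotinib to open-label filgotinib | Filgotinib to SoC | Placebo to SoC |
|---|---|---|---|
| Related to study drug | counted | counted | counted |
| Related to SoC | not counted | counted | counted |
| Study-drug relationship blank | counted | counted | counted |

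Only the middle row differs by column.

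**2. Where post-switch events fall**

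- Protocol 8.5.6: an event up to 30 days after the last study-drug dose is still treatment-emergent for study drug.
- SAP 3.7.1: for men going to SoC, the extension phase starts on the last double-blind dose date plus 1 day.
- SAP 8.1.5.1: double-blind TEAEs stop the day before the extension phase starts, which is the day of the last dose.

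So days 1 to 30 after the last filgotinib dose lie wholly in the filgotinib-to-SoC extension column. If that column reports k men with a related event, the table is compatible with any number from 0 to k having one attributed to filgotinib.

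**3. Illustrative size**

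Let f be the probability that a man in the open-label column has at least one event attributed to study drug, s the probability that a SoC man has one attributed to SoC, and m the probability of an event with a blank relationship. Assume independence, the same m in every column, and no late attribution to earlier study drug.

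- Open-label column: 1 − (1 − f)(1 − m)
- SoC column under the SAP rule: 1 − (1 − s)(1 − m)
- SoC column under a study-drug count that keeps the blank rule: m
- Rise in the SoC column caused by the SoC rule: s(1 − m)

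With s from 5% to 20% and m from 0% to 5%, the rise runs from 0.05 × 0.95 = 4.75 points to 0.20 × 1 = 20 points. It cannot be negative.

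The net difference under the SAP rule, open-label minus SoC, is (f − s)(1 − m):

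- f = 5%, s = 20%, m = 0: −15 points
- f = 10%, s = 10%, any m: 0
- f = 20%, s = 5%, m = 0: +15 points

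Under a study-drug count the difference is f(1 − m). At f = 10% that is 9.5 points (m = 5%) to 10 points (m = 0).

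**4. The blank rule**

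With f = s = 10%, both columns are 10.0% at m = 0. At m = 5% both are 1 − 0.90 × 0.95 = 14.5%. The difference stays at 0.

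**The case against.** The strongest reply is that counting each column's own treatment is a sensible reading of treatment-related. The protocol describes extension treatment as open-label filgotinib or SoC. A study-drug-only row would leave the SoC columns near zero by construction, a distortion the other way. Moreover, Protocol 8.5.6 stops its window 30 days after study drug, so for most of the SoC period SAP 8.1.3 fills a gap and does not contradict the protocol. This stands as an argument for showing SoC-related events. It does not justify merging them with study-drug-related events, least of all within the 30 days that Protocol 8.5.6 does cover.

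A reader might also infer three stronger things that the documents do not support:

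- **That the rule biases the comparison in filgotinib's favour.** It can only raise the SoC columns relative to a study-drug count, but the net sign depends on rates the documents do not give.
- **That blank-equals-related inflates the SoC columns in particular.** It applies to every column and is conservative for filgotinib. It would create an imbalance only if blanks were commoner in SoC men, and nothing in the documents shows that.
- **That filgotinib attribution is lost altogether, or that these are the only filgotinib-specific displays.** SAP 8.1.6 lists all AEs by subject and tabulates events leading to interruption or discontinuation of open-label filgotinib. SAP 8.1.7 gives exposure-adjusted rates for filgotinib. These limit the harm, although the exposure-adjusted rates are organised by exposure and not by attribution.

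Finally, the sequences are selected on Week 13 response and sperm thresholds, and the summaries are descriptive. That also stands and limits the consequence.

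**Conclusion.** The point holds as a defect of definition and labelling in the extension-phase related-AE and related-SAE tables. The meaning of related differs by column, the filgotinib-to-SoC column cannot show how many events were attributed to filgotinib, and the change from the protocol's study-drug wording is not declared. No bias for or against filgotinib is established.

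The 4.75 to 20 point rise in a SoC column rests on assumed rates and the independence model above. What needs no assumed rate is that the rise cannot be negative and that the pooled count cannot be separated from the table alone. The SoC rule does not reach the randomised double-blind safety comparison or any semen endpoint. It should be corrected for the final analysis, but it does not threaten the trial's main conclusion.

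**What to change.** In SAP 8.1.3 and 8.1.6, replace the pooled extension-phase treatment-related row with separate counts in each sequence:

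1. related to study drug, as the protocol defines it;
2. related to SoC, where the eCRF collects that answer;
3. relationship to study drug not recorded, shown as its own count in every sequence.

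Add a footnote that events attributed to background therapy are not counted in the open-label filgotinib column unless that attribution is collected there. Protocol 7.2.1 asks only about IMP and procedures, so the eCRF needs checking on this. Document the departure from Protocol 8.5.6 in the SAP or in the CSR; SAP Section 1 already sends changes made after finalisation to the CSR.

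The cost is slightly longer descriptive AE tables. SAP 8.1.3 indicates that study-treatment and SoC relatedness are recorded as separate answers for men on SoC, so the split should need no new data for them.
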